The main goal of this project is to measure kidney filtration function at day 14 of the ICU stay or the day of discharge from the ICU (whichever occurs first), in order to determine the presence and *magnitude of persistent kidney dysfunction after sepsis episode and to longitudinally assess* further decline of kidney function at one year follow-up. In our initial IRB protocol we have proposed to use iohexol clearance as a gold standard that provides most accurate determination of glomerular filtration rate (GFR). Unfortunately we have not been able to recruit patients into the study as designed due to the complexity of this procedure and need for a dedicated IV line. Since one of the main goals of the overall project is to determine the decline in glomerular filtration rate from the sepsis episode to the one year follow up, we have considered different approaches, in order to be able to obtain this valuable data.

We propose to offer patients four complementary ways for GFR assessment, both at approximately day 14 or approximately at the day of discharge from the ICU and at the one year follow up :

1. Determine clearance of iohexol from blood after iohexol injection and/or
2. Determine appearance of iohexol in urine after iohexol injection (this would be the same injection as in one, and would not require two injections) and/or
3. A timed urine collection to determine clearance of urea and creatinine and/or
4. Estimated GFR using calculations with serum creatinine, if performed clinically if not we will draw it specifically for the study, and cystatin C, performed specifically for the study. Currently any patient that is enrolled in this protocol will already be a part of IRB201400611 and will already be getting serum creatinine, cystatin C and a urine microalbumin/creatinine ratio drawn at the one year appointment.

This approach will allow us to maximize recruitment of patients into the study by providing flexibility, but it also provides an important opportunity to validate the different measurements against the gold standard, iohexol clearance. For all patients we will also obtain a urine microalbumin/creatinine ratio as another important determinant of structural kidney damage.

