We also propose to include stage 3 AKI patients on renal replacement therapy, who were previously excluded. Some of these patients do recover after initial episode and will present at one year follow up. It will be very valuable for us to understand factors leading to recovery. For these patients we will use only methods 2 and/or 3 for estimation of GFR, both of which are safe. Even patients who are dialysis dependent have some level of residual renal function and even if they make even a minimal amount of urine this may be an important determinant of renal recovery.

The assessments will be performed approximately 72 hours within day 14 or the anticipated discharge from the ICU and at 1 year follow-up.

Given the loss of muscle mass in chronic critical illness, we will measure, rather than estimate glomerular filtration rate, to determine whether unrecognized kidney dysfunction in late sepsis drives inflammation and catabolism, contributing to poor long term survival and development of chronic kidney disease. For the assessment of glomerular filtration rate, the most frequently used clinical test is serum creatinine, despite the fact that its accuracy depends on a constant muscle mass, which is almost never the case with patients with chronic critical illness. We have previously demonstrated that sepsis and chronic critical illness are associated with a rapid and significant loss of lean muscle mass over time. Even a small fall of 25% in muscle mass should lead to a fall in serum creatinine of 25%. Thus in a chronic critical illness patient hospitalized for 4 weeks, the persistent increase in serum creatinine from a baseline of 1.0 mg/dl to 1.5 mg/dl implicates a significant drop in glomerular filtration rate; assuming a 50% reduction in muscle mass, in this individual a serum creatinine of 1.5 would reflect glomerular filtration rate of ~ 37 mL/min/1.73 m², consistent with stage 3 chronic kidney disease. To determine whether unrecognized decline in kidney function contributes to persistent inflammation, decreased protein intake, and muscle wasting in chronic critical illness it is necessary to measure glomerular filtration rate rather than estimate it.

5. Specific Aims:

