Iohexol clearance will not be performed in patients with a known allergy to contrast. All patients will need two IVs for this procedure. If the subject does not have 2 intravenous catheters (IVs) as a part of their routine clinical care during sepsis episode they will be placed by someone from the research team. We will attempt to place a 22 gauge or larger IV as indicated by the patients veins. We will inject iohexol 0.5-1 ml of iohexol diluted in normal saline through an existing IV catheter, and we will collect no more than 3 ml of blood prior to the injection and at approximately 1, 2, 3 and 4 hours after injection. The concentration of iohexol in the blood will be measured by ELISA (Biopal Inc). The GFR will be calculated by the blood clearance method:

The concentration of iohexol ($\mu\text{g}/\text{ml}$) in each blood sample will be plotted as a function of time. The data will be fit to a one exponential decay function, i.e., $Y = B e^{-bX}$. The function will be integrated over the limits zero to infinity to obtain the area-under-the-curve (AUC), i.e., $AUC = B/b$ ($\text{mg}\cdot\text{min}/\text{ml}$). The GFR value (ml/min) is then obtained by dividing the administrated dose by the AUC (REF:

2. Timed urinary collection for combined urea and creatinine clearance.

The urine will be collected for at least 4 hours to as long as 24 hours or more. The urine volume determined and a sample sent to the lab for determination of creatinine and urea concentration. We will not place a foley if there is not a foley and the person will only be asked to collect their urine for the indicated time.

3. Estimation of GFR using serum creatinine and cystatin C. We will estimate GFR using both serum creatinine and cystatin C and average the two values using CKD-EPI equation.

The glomerular filtration rate at 1 year will be compared to the measured glomerular filtration rate at discharge and the rate of change in glomerular filtration rate over time will be determined. The measured iohexol glomerular filtration rate will be compared to the estimated glomerular filtration rate, as determined by the in order to correlate the equation after adjusting for loss of muscle mass.

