The patients will be asked to return for a one year follow up appointment that will occur with the one year appointment from IRB protocol #2014-611 at the Institute on Aging. The patients will receive a \$25 compensation for the inpatient portion of the study and a \$75 compensation for their time when they return for the one year follow up visit. At one year follow-up all measurements for iohexol clearance, will be performed in CTSI. Timed urine collection at one year follow up will be performed at home and all necessary supplies will be mailed to patient. If the patient did not do a timed collection, but is still willing to perform timed urine at the time of the CTSI visit, we will time the urine collection during their CTSI visit. For patients who opt only for serum creatinine/cystatin C measurement and spot urine microalbumin/creatinine ratio, urine and blood will be collected in the CTSI as a part of the IRB protocol #2014-611.

Primary Outcomes

We will compare:

Protocol

IRB version 03.09.04

PI version 9/10/2015

- a) The decline in glomerular filtration rate at 1-year follow-up between chronic critical illness and control groups.
- b) Correlation between iohexol glomerular filtration rate and estimated glomerular filtration rate using previously validated equation applied to serum creatinine.
- c) Development of de novo albuminuria or progression of existing albuminuria.

Data Collection and Analyses

All relevant clinical and laboratory variables for this cohort will be uploaded directly into the REDCap case report form (CRF) from the EPIC EMR for the main STUDY IRB#2014-611.

Sample size and feasibility. Assuming that chronic critical illness patients have at least a two-fold decline in glomerular filtration rate as compared to the average glomerular filtration rate decline of 6 ± 16 ml/yr, the sample size of 150 chronic critical illness and 80 control subjects will offer 80% power at a two-sided significance of $P=0.05$.

Data analyses and interpretation. The parametric and non-parametric tests for difference between two independent samples will be used to compare decline in glomerular filtration rate between chronic critical illness. Using the Cox survival model we will test the multivariate relationship between glomerular filtration rate at day 14 and survival status at year 1.

Protection of Privacy and Confidentiality

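### Primary outcome (b) judges creatinine eGFR against iohexol GFR by correlation alone, which cannot show the overestimation the protocol expects

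*Combined protocol and SAP*

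**What the plan says.** Primary Outcomes (b) is the "Correlation between iohexol glomerular filtration rate and estimated glomerular filtration rate using previously validated equation applied to serum creatinine". The type of coefficient is not given. The paragraph headed Data analyses and interpretation covers two-sample tests of GFR decline and a Cox model for survival; it contains nothing on (b).

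One other place describes the comparison. At the end of the section on estimating GFR from serum creatinine and cystatin C, the protocol says the iohexol value will be compared with the estimate, and the stated purpose is "in order to correlate the equation after adjusting for loss of muscle mass". Words are missing from the extracted text just before this, apparently the name of the equation.

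Two statements in 4. Background show what the comparison is for:

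- On offering four methods of GFR assessment: "it also provides an important opportunity to validate the different measurements against the gold standard, iohexol clearance".
- On why creatinine cannot be trusted in these patients: "Even a small fall of 25% in muscle mass should lead to a fall in serum creatinine of 25" per cent. A worked example follows, with 50% muscle loss, in which "a serum creatinine of 1.5 would reflect glomerular filtration rate of ~ 37 mL/min/1.73 m²".

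**The concern.** Validating one measurement against a gold standard asks how far, and in which direction, the two disagree. Correlation asks only how closely the points follow a straight line, whatever its slope or intercept. The Background predicts a systematic error in one direction: creatinine eGFR reads too high after muscle loss. A uniform proportional error of that kind leaves Pearson r untouched.

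One of the three listed primary outcomes could therefore be reported exactly as planned, with a high r read as successful validation, without showing whether creatinine eGFR reads high in these patients. That possibility is the protocol's own reason for measuring GFR instead of estimating it.

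**Working it through.** **1. The protocol's own example.** Inputs from 4. Background: creatinine rises from 1.0 to 1.5 mg/dl, muscle mass falls by 50%, true GFR is about 37. The baseline GFR is not given. Taking GFR as proportional to (remaining muscle)/(creatinine):

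- true GFR = baseline × (1.0/1.5) × 0.5
- a baseline of 111 gives 111/1.5 × 0.5 = 37, the stated figure; baselines of 90 to 120 give 30 to 40
- without allowing for muscle loss, the creatinine value would be 111/1.5 = 74, twice the true GFR.

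The protocol's example thus implies a twofold overestimate. Its milder case of 25% loss implies 1/(1 − 0.25) = 1.33. If eGFR varies as creatinine to a power between −0.8 and −1.2, that 1.33 becomes 1.26 to 1.41.

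**2. Algebra.** For any constant a > 0, corr(aX, Y) = corr(X, Y). Factors of 1, 1.33 and 2 all give the same r. This needs no assumption about the data.

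**3. Illustration.** Assumed, because the documents give no values: true GFR normal with mean 60 and SD 20, kept above 10; iohexol = GFR × exp(N(0, 0.05)); eGFR = GFR × f × exp(N(0, 0.15)). The SD of the log ratio is √(0.15² + 0.05²) = 0.158, and the limits of agreement are ratio × exp(±1.96 × SD of the log ratio).

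| Scenario | r | Mean ratio | Limits of agreement | Mean difference (ml/min) | Within 30% |
|---|---|---|---|---|---|
| No error, f = 1 | 0.89 | 1.00 | 0.73–1.36 | +0.6 | 94% |
| 25% muscle loss, f = 1.33 | 0.89 | 1.33 | 0.98–1.82 | +21 | 44% |
| Loss varying 0–25% | 0.86 | 1.15 | 0.81–1.63 | +9.8 | 75% |
| No error, eGFR noise 0.17 | 0.86 | 1.00 | – | +0.8 | – |

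Rows 1 and 2 share an r but differ by a third in the ratio. Rows 3 and 4 show that when muscle loss varies between patients r does fall, but slightly noisier unbiased estimates lower it by the same amount.

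**4. Dependence on spread.** With the error fixed at 1.33, a GFR SD of 10 gives r = 0.71 and an SD of 30 gives r = 0.93. The value of r partly reflects how varied the recruited patients are.

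**5. Would a ratio be estimable with few pairs?** The number of iohexol pairs is not stated. The Background says of the earlier iohexol-only design: "Unfortunately we have not been able to recruit patients into the study as designed due to the complexity of this procedure". Of patients on renal replacement therapy it says: "For these patients we will use only methods 2 and/or 3 for estimation of GFR", which leaves them without blood iohexol clearance. Expected 95% CI = exp(ln 1.333 ± t(n−1) × SD/√n):

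| Pairs | SD of log ratio 0.158 | SD 0.304 (eGFR noise 0.30) |
|---|---|---|
| 10 | 1.19–1.49 | 1.07–1.66 |
| 20 | 1.24–1.44 | 1.16–1.54 |
| 50 | 1.28–1.40 | – |

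For n = 10 in the first column, t = 2.262 and the half-width is 2.262 × 0.158/√10 = 0.113 on the log scale. Even 10 pairs would be expected to separate a ratio of 1.33 from 1.

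**The case against.** Five points can be made for the plan.

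*The text may say more than survives.* The protocol also uses the verb compare, and the one methods sentence has a gap. An agreement measure in the missing words cannot be strictly excluded. But the purpose that survives in that sentence is again correlation, and the definition of (b) under Primary Outcomes is complete. The point is limited to the readable text.

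*The coefficient is not specified.* The calculations above use Pearson r. Spearman's coefficient behaves the same way, at about 0.89 in rows 1 and 2. A concordance coefficient would respond, falling from 0.88 to 0.61, but as a single number it still does not say whether eGFR reads high or low, or by how much.

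*Adjustment for muscle loss is planned.* In the 0–25% scenario, perfect adjustment would bring r back from 0.86 to 0.89, which random noise would not do, so the adjusted analysis carries some information. It gives no size, however; it could remove the very error at issue; and the documents name neither a model nor a muscle measure for it.

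*A pooled ratio dilutes the effect.* If chronic critical illness patients read 1.33 and controls 1.00 (assumed), the planned 150:80 mix gives exp((150/230) × ln 1.333) = 1.21. This stands, and is why the group breakdown must accompany the overall figure.

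*The estimate itself is ambiguous.* Outcome (b) uses creatinine alone, while the methods section averages creatinine and cystatin C estimates. If cystatin C were unaffected by muscle (assumed), the averaged estimate would be off by (1.33 + 1.00)/2 = 1.17. The revised wording should say which estimate is meant; the definition of (b) points to creatinine.

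**Conclusion.** The concern holds. The only measure named for (b) cannot answer the validation question for which the paired data are collected. That r is blind to a uniform proportional error is algebra. The size of what would be missed, about a third at 25% muscle loss and a factor of two in the protocol's own example, rests on the Background's link between muscle and creatinine and on eGFR varying roughly as 1/creatinine. The values of r, the within-30% shares and the interval widths rest on the assumed GFR distribution and noise, and are illustrations.

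The impact is limited. The main goal in 5. Specific Aims lies elsewhere, and neither the GFR-decline comparison nor the Cox model uses (b). The change should be made, because (b) is a primary outcome and the remedy is cheap, but the study does not stand or fall on it.

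**What to change.** Redefine (b) along these lines:

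- **Lead measure:** the geometric mean ratio of creatinine eGFR to iohexol GFR, analysed on the log scale, with 95% CI and log-scale limits of agreement, unadjusted for muscle loss.
- **Scale:** put both GFRs on one stated scale. The section on iohexol clearance works in absolute units ("The GFR value (ml/min) is then obtained by dividing the administrated dose by the AUC"), whereas the Background example is per 1.73 m². A mismatch would itself enter the ratio.
- **Estimate:** state that the eGFR in (b) is the creatinine-based one and name the equation.
- **Reporting:** overall at each visit, always accompanied by a descriptive breakdown into chronic critical illness and control groups, with the number of pairs.
- **Supporting measures:** the share of eGFR values within 30% of iohexol GFR; r kept as description, with the type of coefficient stated.
- **Muscle-adjusted comparison:** secondary, and only once a muscle measure and a model are specified.

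The cost is revised wording and a little more analysis of pairs already being collected, with no extra samples or visits. A common scale needs height and weight, assumed to be available. With few iohexol pairs the interval will be wide, and wider still within groups; the report should say so.

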The goal of this study is to determine to what extent persistent kidney dysfunction contributes to inflammation, catabolism and long-term mortality in chronic critical illness. We will test the working hypothesis that persistent kidney damage in chronic critical illness contributes to decreased survival through persistent inflammation, immunosuppression and catabolism.

6. Research Plan:

Study overview and design

This is a prospective, longitudinal, case-control study involving a subset of the initial cohort of 400 sepsis subjects enrolled in IRB STUDY #2014-611 who agree to measurement of glomerular filtration rate using iohexol clearance and the amended measurements listed above. Assuming a minimum 70% recruitment rate, we expect to enroll minimum of 230 patients and maximum of 400.

Identifying patients and consent

All sepsis patients who consent to enroll in the IRB Project #2014-611 and meet inclusion/exclusion criteria will be asked for enrollment in this study after they are consented for the IRB Project #2014-611. The informed consent will be obtained by the same research staff

within the Human Subject Core of the University of Florida P50 Center. Since many sepsis patients in the surgery and trauma ICUs may have altered mental status or pharmacologic sedation, but would be regarded as prospective research subjects a legal authorized relative (LAR) or next of kin would be approached for informed consent. The research nurse will monitor the patient's progress and once they regain capacity, the patient will be reconsented.

Inclusion Criteria

- a) Presence in the surgery or trauma ICU where clinical care can be managed by surgical critical care guided by standard operating procedures.
- b) Age of ≥ 18 years
- c) First entrance into our sepsis protocol at Shands/UF on index admission.
- d) Ability to obtain informed consent.

Exclusion criteria

Expected lifespan of the patient is less than 3 months due to severe pre-existing comorbidities (ex. recurrent, advanced or metastatic cancer).

- b) Severe traumatic brain injury (evidence of neurologic injury on CT scan and a GCS <8)
- c) refractory shock (i.e., patients who die within 12 hours)
- d) uncontrollable source of sepsis (e.g., irreversible disease state such as unresectable dead bowel)
- e) Patient or patient's family are not committed to aggressive management of the patient's condition.
- f) severe CHF (NY Heart Association Class IV)

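### The stated 80% power for the decline in GFR comes to about 77% on its own inputs, no SD is given for the chronic critical illness group, and the unnamed two-sample test should be fixed as Welch's.

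*Combined protocol and SAP*

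**What the plan says.** All the relevant text is in section 6 (Research Plan) of the combined protocol and SAP.

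- **Primary Outcomes, item (a):** "The decline in glomerular filtration rate at 1-year follow-up between chronic critical illness and control groups".
- **Sample size and feasibility:** the assumption is that "chronic critical illness patients have at least a two-fold decline in glomerular filtration rate", set against an "average glomerular filtration rate decline of 6 ± 16 ml/yr". From this, "the sample size of 150 chronic critical illness and 80 control subjects" "will offer 80% power at a two-sided significance of" 0.05.
- **Data analyses and interpretation:** "The parametric and non-parametric tests for difference between two independent samples will be used" to compare the decline. This is the only analysis text for outcome (a).
- **Study overview and design:** "we expect to enroll minimum of 230 patients and maximum of 400".

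The plan gives no SD for the CCI group. It does not say whether the parametric or the non-parametric test is primary, or whether the parametric test pools the variances.

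**The concern.** The power statement rests on a single spread attached to the average decline, although the two groups are defined by different clinical courses and are assumed to decline at different rates. There are three things to settle: whether the stated inputs give the stated power, how far the power depends on the missing CCI SD, and whether the choice of test matters.

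The last question arises because the groups are unequal, at 150 to 80. With equal groups of this size, a pooled t test tolerates unequal SDs well. With unequal groups it does not. If the larger group is the more variable, the pooled standard error is too large and the test is conservative. If the smaller group is the more variable, the pooled standard error is too small and the test rejects too often. The rank test is affected in the same directions, though less strongly. Leaving the test unnamed for a primary outcome therefore leaves its error rate open, and allows the choice between two p-values to be made after the data are seen.

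**Working it through.** **Inputs from the protocol.** Control decline 6 ml/yr; CCI decline 2 × 6 = 12, so the difference is 6; spread 16, read as an SD; n = 150 CCI and 80 control; two-sided 0.05; stated power 80%.

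**Input not in the protocol.** The SD of decline in CCI. Values other than 16 below are assumptions, as is any control SD other than 16.

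**Step 1: the plan's own figure, SD 16 in both groups.**

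- SE = 16 × √(1/150 + 1/80) = 16 × 0.1384 = 2.215.
- Power = Φ(6/2.215 − 1.960) = Φ(0.749) = 77.3%. The noncentral t with 228 df gives 77.0%, and a rank test about 75%.
- The stated 80% is not reproduced. At the same allocation it needs n(control) = (1 + 1/1.875) × 16² × (1.960 + 0.842)² / 6² = 85.6. That is 86 controls and 1.875 × 86 = 161.25, or 162 CCI patients.
- At 150 v 80 it would instead need a difference of 6.2 or an SD of 15.5. An equal split of the same 230 patients (115 v 115) would give 81.2%.

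**Step 2: unequal SDs.** Write s1 for the CCI SD and s0 for the control SD.

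- True SE: SE_true = √(s1²/150 + s0²/80).
- SE used by the pooled test: SE_pool = √{[(149·s1² + 79·s0²)/228] × (1/150 + 1/80)}.
- With k = SE_pool/SE_true, the pooled test has size 2[1 − Φ(1.96k)] and power about Φ(6/SE_true − 1.96k).
- Welch's power comes from the noncentral t with noncentrality 6/SE_true and Satterthwaite degrees of freedom.

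Example, SDs 32/16:

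- SE_true = √(1024/150 + 256/80) = √10.03 = 3.17.
- SE_pool = √(757.9 × 0.01917) = 3.81, so k = 1.204.
- Size = 2[1 − Φ(2.36)] = 1.8%.
- Pooled power = Φ(1.895 − 2.359) = 32%.

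Example, SDs 16/32:

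- SE_true = √(256/150 + 1024/80) = √14.51 = 3.81.
- SE_pool = √(522.1 × 0.01917) = 3.16, so k = 0.831.
- Size = 2[1 − Φ(1.63)] = 10.4%.

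| CCI SD / control SD | Pooled t size | Rank test size (simulated) | Pooled t power | Welch power |
|---|---|---|---|---|
| 12 / 16 | 7.2% | 6.3% | 87% | 83% |
| 16 / 16 | 5.0% | 5.4% | 77% | 77% |
| 20 / 16 | 3.6% | 4.1% | 65% | 69% |
| 24 / 16 | 2.7% | 3.7% | 52% | 61% |
| 32 / 16 | 1.8% | 3.1% | 32% | 47% |
| 16 / 24 | 8.2% | 6.6% | – | – |
| 16 / 32 | 10.4% | 8.5% | – | – |

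Simulation with normal data agrees: pooled size 1.8% at 32/16 and 10.1% to 10.6% at 16/32, with Welch between about 4.7% and 5.2% across the scenarios. The pooled power at 12/16 is not a real gain, because it comes with a size of 7.2%.

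**Step 3: what the test choice can and cannot recover.** From SD 16 to 24 in CCI, Welch's power falls by about 15 points (76.8% to 61.5%), and pooling costs about 9 more. From 16 to 32, Welch's power falls by about 30 points (76.8% to 47.1%), and pooling costs about 15 more. Most of the loss comes from the spread itself.

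**The case against.** **The plan does not name a pooled t test.** This stands. Welch's test is also a parametric two-sample test, so the text is consistent with it. The defect is that the test is not specified. A reader might infer that the plan has committed to a test with the wrong error rate, and the text does not show that.

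**Nothing in the documents shows that CCI is more variable.** This also stands. A reader might argue that a doubled mean decline brings a larger spread. It does not follow: a uniform extra loss of 6 ml/yr would leave the SD at 16, and a spread already 2.7 times the mean (16/6) is evidently not driven by the mean. The inclusion of patients on renal replacement therapy and the four GFR methods are not confined to CCI in the text. Noise added to both groups raises a common SD, which no choice of two-sample test cures: at SD 24 in both groups, either test has about 43% power.

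**The figures are floors.** The assumed effect is a minimum and enrolment could reach 400, where the same split and equal SDs would give about 95%. But the 80% is claimed specifically for 150 v 80 and a two-fold decline, and that is the claim checked here.

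**What remains.** The equal-SD assumption is unstated and unsupported in either direction, the stated power is about three points too high even under it, and the test is open.

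**Conclusion.** The point holds as a misstated power figure and an under-specified primary test. On the protocol's inputs, 150 v 80 gives about 77%, not 80%; this assumes that the ± term is an SD, that it applies to both groups, and that the average decline of 6 represents the controls. A pooled t test at these group sizes would have a true error between about 1.8% and 10% for SD ratios up to two in either direction, while Welch's test holds about 5%. The CCI SDs behind those figures are hypothetical.

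Two further inferences should be resisted:

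- Equal SDs are not the most favourable case. With the control SD at 16, Welch's power is about 80% at a CCI SD of 14 and 83% at 12.
- Welch's test does not preserve the planned power. It protects the error rate and avoids the extra loss from pooling when CCI is more variable, but its own power still falls to about 47% at a CCI SD of 32. Inflated false positives arise only if the controls are the more variable group.

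**What to change.** In Data analyses and interpretation, name Welch's unequal-variance t test, with its 95% CI for the difference in decline, as the primary analysis of outcome (a). If the comparison is made by regression, use heteroscedasticity-robust standard errors. State that the rank test is supportive.

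In Sample size and feasibility, give an SD for each group with its basis. Restate the power for 150 v 80 as about 77% at equal SDs of 16, followed by a range marked as assumption (Welch, control SD 16): about 83% at a CCI SD of 12, 69% at 20, 61% at 24 and 47% at 32.

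The cost is a few sentences. At equal SDs Welch's test gives 76.8% against 77.0% for the pooled test, and no patients or procedures are added. If the sponsor wishes to keep 80% at the same allocation, about 162 v 86 are needed with equal SDs of 16. With Welch's test it would be about 192 v 103 at a CCI SD of 20, or 231 v 123 at 24. That is a separate decision.

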For the current study we have developed additional data and safety monitoring plan. The study involves more than minimal risk related to intervention for the routine standard measurement of glomerular filtration rate using iohexol. In addition, the study includes patients with a highly morbid pre-existing medical disease (sepsis), some of who are vulnerable subjects (chemically sedated in ICU due to primary disease sepsis). Thus physical, social, psychological, or financial events that are anticipated due to subjects' pre-existing disease including debilitated state, acute kidney injury, prolonged hospitalization, incapacity and death are possible and will be treated by the standard clinical care.

Safety and data integrity for this study will be assessed by PIs and the P50 investigator team led by program director [name] at weekly Adjudication meetings, IRB, GCRC Data Safety Monitoring Subcommittee and Internal Medical monitors for entire P50 program ([name], M.D., Professor of Surgery; [name], M.D., Professor of Anesthesiology, UF (Gainesville)). Accumulating study-wide data across all subjects will be monitored weekly and discussed at the weekly P50 meeting. Accumulated data will be discussed every three months at the P50 safety meeting. The following safety endpoints are in place: An MD is required to perform every injection and observe the patient for at least 15 minutes. If a side effect occurs as a result of the injection, we will formally present the case at the P50 weekly meeting. Importantly, the iohexol used for GFR measurement is routinely used clinically and we are using a 1/10 to 1/100 of the dose that is routinely used clinically, thus risks of side effects are greatly reduced. In addition the majority of these patients would have already received at least one contrast study during their hospitalization making it extremely unlikely to have undetected allergy to contrast. With any side effect suspected to occur as the result of the GFR determination, we will stop further GFR studies until the event can be presented and discussed at the weekly P50 meeting. Following adverse events will be observed: shortness of breath, itching, hives, vomiting, swelling, breathing difficulties, hypotension or any other noted problem related to the injection. They will be identified and monitored using advance monitoring system in ICU and GCRC as summarized in the table below

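### The 230 patients behind the 80% power are also the minimum enrolment, with no allowance for death or non-return before the one-year GFR

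*Combined protocol and SAP*

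**What the plan says.** Under Sample size and feasibility, the protocol assumes that "chronic critical illness patients have at least a two-fold decline in glomerular filtration rate" relative to an "average glomerular filtration rate decline of 6 ± 16 ml/yr", and concludes that "the sample size of 150 chronic critical illness and 80 control subjects will offer 80% power at a two-sided significance of" 0.05. The two groups add up to 230.

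Under Research Plan, Study overview and design, the same number is the enrolment floor: "Assuming a minimum 70% recruitment rate, we expect to enroll minimum of 230 patients and maximum of 400".

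The comparison being powered is primary outcome (a): "The decline in glomerular filtration rate at 1-year follow-up between chronic critical illness and control groups". It needs a GFR near day 14 or ICU discharge and another at the one-year visit.

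The plan expects deaths. The Data and safety monitoring plan says that "acute kidney injury, prolonged hospitalization, incapacity and death are possible and will be treated by the standard clinical care". Data analyses and interpretation specifies a Cox model for "the multivariate relationship between glomerular filtration rate at day 14 and survival status at year 1". No section gives a rate for death, withdrawal or non-return, or an inflation of the sample size. The 70% is a recruitment rate, not a retention rate.

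**The concern.** A patient who dies or does not come back has no one-year GFR and so no observed decline. A power figure for this outcome therefore refers to patients measured at both times. The plan does not say whether 150 and 80 are enrolled or evaluable patients, and it uses their sum as the minimum to enrol. At that minimum, the stated power requires that nobody is lost over a year, in a sepsis cohort whose survival is itself under study.

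Loss may also be uneven. The working hypothesis is that persistent kidney dysfunction in chronic critical illness (CCI) reduces survival, so CCI patients may be lost more often than controls. As written, a reader cannot tell what enrolment and follow-up the 80% depends on.

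**Working it through.** **Inputs.** From Sample size and feasibility: n = 150 (CCI) and 80 (control), two-sided 0.05, reference decline 6 ml/yr. Two readings are assumed: two-fold means 12 against 6, so the difference Δ is 6 ml/yr; and ±16 is an SD (σ) that applies in both groups. The documents give no loss rate, so total losses of 10, 20 and 30% are assumptions.

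**Formula.** SE = σ√(1/n₁ + 1/n₂); power = Φ(Δ/SE − 1.960).

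**The plan's own figure, no loss.** SE = 16√(1/150 + 1/80) = 2.215. Δ/SE = 6/2.215 = 2.709. Power = Φ(0.749) = 77.3%; the noncentral t with 228 df gives 77.0%. The stated 80% is missed by about 3 points. A difference of 6.21 (t: 6.23) or an SD of 15.47 (t: 15.40) would give 80%.

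**Loss at 230 enrolled (normal approximation).** The last column resets σ to 15.47, so that 150 and 80 give exactly 80% before any loss.

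| Total loss | Where | CCI / control left | SE (σ = 16) | Power, σ = 16 | Power, σ = 15.47 |
|---|---|---|---|---|---|
| 10% | equal | 135 / 72 | 2.335 | 72.9% | 75.7% |
| 20% | equal | 120 / 64 | 2.477 | 67.8% | 70.7% |
| 30% | equal | 105 / 56 | 2.648 | 62.0% | 65.0% |
| 10% | CCI only (23) | 127 / 80 | 2.284 | 74.8% | 77.6% |
| 20% | CCI only (46) | 104 / 80 | 2.379 | 71.3% | 74.2% |
| 30% | CCI only (69) | 81 / 80 | 2.522 | 66.2% | 69.2% |

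The difference detectable with 80% power at σ = 16 is (1.960 + 0.842) × SE. It rises from 6.21 ml/yr with no loss to 6.54, 6.94 and 7.42 (equal), or 6.40, 6.67 and 7.07 (CCI only).

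**More favourable inputs.** With σ = 16 and no loss, a difference of 6.5 gives 83.5% and a difference of 7 gives 88.5%. At the edge of rounding (Δ = 6.5, σ = 15.5), power without loss is 85.7%, and 80% holds at 230 enrolled up to about 14% equal loss or 21% total loss confined to CCI.

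**Room above the floor.** Let k = (1.960 + 0.842)² × 16²/6² = 55.8. At 150:80, 80% power needs k(1 + 150/80) + k(1 + 80/150) = 160.5 + 85.6 = 246 evaluable patients (248 by the t distribution). Break-even equal loss is therefore:
- 280 enrolled: 1 − 246/280 = 12.1% (t: 11.4%)
- 400 enrolled: 1 − 246/400 = 38.5% (t: 38.0%)

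With all loss in CCI, the break-even total loss is about 18% at 280 and 42% at 400.

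**The case against.** Several points in the plan's favour are sound.

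- **The 77% is not clearly an error.** The inputs are printed as rounded whole numbers, and the effect is described as at least two-fold, so 77% is power at the smallest assumed effect. A true difference of 7 would still give 80.7% at 230 enrolled after 20% equal loss. This stands, and it means that whether loss takes power below 80% depends on the true difference and SD. But the plan states 80% for 150 and 80. On that statement, any loss at the floor goes below it; only more favourable inputs, which the plan does not state, avoid this.
- **230 is a floor, not the target.** At 400 enrolled there is ample room. Also, 70% of the 400-patient parent cohort is 280, and a fall from 280 to 230 would be a loss of 17.9%, so 150 and 80 might have been meant as evaluable numbers. The documents do not say so: 230 is given as the number to enrol, and the range is nowhere linked to attrition.
- **Retention is supported.** Creatinine and cystatin C are already drawn at the parent study's one-year visit, urine can be collected at home, the return visit is paid, and patients with a short expected lifespan are excluded. These steps may reduce non-return and some early deaths. They cannot supply a one-year GFR for a patient who has died.
- **The break-evens at 280 and 400 assume the 150:80 split.** The Background says about a third of early sepsis survivors follow the CCI course. If a third of those enrolled were CCI (an assumption), the break-even total loss confined to CCI would be about 5% at 280 and 16% at 400. This caution is fair, and it makes the position weaker rather than stronger. The 30% CCI-only case, which removes 69 of 150 CCI patients and no controls, is an extreme scenario.

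**Conclusion.** The concern holds. The number that carries the 80% power is also the minimum enrolment, and nothing is set aside for death or non-return before the measurement that the primary comparison needs. At 230 enrolled, assumed losses of 10 to 30% cost roughly 4 to 15 points if equal in both groups and 2 to 11 points if confined to CCI, relative to the no-loss power on the same inputs. Resulting power is 62 to 75% at a difference of 6 and SD 16, or 65 to 78% on inputs set to give exactly 80% without loss.

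The result rests on a common SD of 16, a difference of 6 and loss rates that are assumptions. The 3-point shortfall with complete follow-up is within rounding and is not the main issue. Enrolment well above the floor could resolve the problem, but the plan does not show that. This should be fixed; it does not invalidate the design.

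**What to change.** 1. Restate the power for evaluable patients: 150 CCI and 80 controls with a GFR at both index and one year give 77% power for a difference of 6 ml/yr (80% for about 6.2 ml/yr), with SD 16 and two-sided 0.05. Alternatively, print the unrounded inputs that give 80%.
2. State the expected one-year loss from death and from non-return, separately for CCI and controls, with the source. Give a short table of power at the resulting evaluable numbers for enrolment from 230 to 400, using the expected split between groups.

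A minor addition would be the denominator of the 70% recruitment rate, since 70% of 400 is 280 and 230 is 70% of about 329.

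The cost is a few sentences and one table, with no extra patients or procedures. The drawback is that the stated power will look less favourable at the lower end of enrolment.
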